6.0 Study Product Description

Formulation, Packaging, and Labeling

FDA-approved estradiol or placebo vaginal cream will be provided. The product will be labeled as to "Topical Vaginal Cream for Use on Study" and will be identifiable as to estrogen or placebo with a specific code number. Participants and the study physicians are blinded as to estrogen or placebo until data analysis completion.

Product Storage and Stability

Store at room temperature. Protect from temperatures in excess of 40° C (104° F). Store in original packaging until just before use. Store away from heat, moisture and light. Once product is opened, the product should be used within 90 days.

Dosage, Preparation and Administration

Estradiol vaginal cream 0.5 g vaginal daily or placebo vaginal cream will be applied vaginal daily from study day 1 every day until 2 days before scheduled surgery.

Topical estradiol is poorly absorbed systemically. In this study, subjects will be on a small topical dose of estradiol for a limited time period. In addition, the use of topical estrogen in this study is consistent with common clinical practice for treatment of vaginal atrophy before pelvic organ prolapse surgery.

In order to maintain double-blind, the estradiol and placebo cream will be formulated by a compounding pharmacy. The estradiol vaginal cream will contain 0.01% of estradiol and the placebo vaginal cream will contain the excipients only that are included in the estradiol vaginal cream.

Modification of Study Intervention for Participant

We don't anticipate any dose adjustments due the minimal time of study use.

Accountability Procedures for the Study Intervention

After randomization to vaginal cream vs. placebo, subjects will be given cream in an amount anticipated to last the duration of the study period. If the subject needs a replacement cream, that will be provided. Unused product will be stored during active shelf life and then disposed of.

Assessment of Subject Compliance

Compliance with the study intervention will be determined by study diary.

Patients will be asked to returned unused cream at end of study period to further measure compliance.

Concomitant Medications/Treatments

Any medications the subject takes are permitted with the exception of sex hormone replacement in postmenopausal women.

7.0 Potential Risks and/or Discomforts of Participation

Topical Vaginal Cream: Allergic reaction; Irritation or other discomfort; Vaginal burning; Vulvar-vaginal infection; Vaginal bleeding; Increased vaginal discharge; Trauma from applicator; Headache; Breast tenderness.

OCT – Possible discomfort with the probe in connection with the evaluation. Some women have reported minor irritation, redness and vaginal bleeding.

Pelvic floor (endovaginal) ultrasound – The test is usually painless although some women have reported mild discomfort from the pressure of the probe. There are no known harmful effects on humans.

Blood Draw – The discomfort associated with drawing blood from a vein is a light pinch or pinprick at the puncture site. The risks include possible bruising and swelling around the puncture site; less commonly, infection, small blood clot or bleeding at the puncture site and faintness from the procedure.

8.0 Adverse Events or Unanticipated Problems

Any adverse event (AE) or unanticipated problems considered serious by the PI or study clinician will be reported to the IRB in accordance with IRB policies and procedures.

- All deaths and immediately life-threatening events, whether related or unrelated, will be recorded
 on the Serious Adverse Event (SAE) Form and sent by fax within 24 hours of site awareness.
- SAEs or unanticipated problems other than death and immediately life-threatening events, regardless of relationship, will be reported via fax by the site within 72 hours of becoming aware of the event.

AEs will be graded for severity and relationship to study participation.

Severity of Event: All AEs will be assessed by the clinician using the following guidelines to quantify intensity.

- Mild: events require minimal or no treatment and do not interfere with the patient's daily activities.
- Moderate: events result in a low level of inconvenience or concern with the therapeutic measures. Moderate events may cause some interference with functioning.
- Severe: events interrupt a patient's usual daily activity and may require systemic drug therapy or other treatment. Severe events are usually incapacitating.
- Life threatening: any adverse drug experience that places the patient or subject, in the view of the investigator, at immediate risk of death from the reaction as it occurred, i.e., it does not include a reaction that had it occurred in a more severe form, might have caused death.

Relationship: The clinician's assessment of an AE's relationship to the study article is part of the documentation process, but it is not a factor in determining what is or is not reported in the study. If there is any doubt as to whether a clinical observation is an AE, the event should be reported. All AEs must have their relationship to study product assessed using the terms: associated or not associated. In a clinical trial, the study product must always be suspect. To help assess, the following guidelines are used.

- Associated The event is temporally related to the administration of the study product and no other etiology explains the event.
- Not Associated The event is temporally independent of study product and/or the event appears to be explained by another etiology.

Serious Adverse Event (SAE): An SAE is defined as an AE that meets one of the following conditions:

- Death during the period of protocol defined surveillance
- Life-threatening event (defined as a subject at immediate risk of death at the time of the event)
- An event requiring inpatient hospitalization or prolongation of existing hospitalization during the period of protocol defined surveillance
- Results in congenital anomaly or birth defect
- Results in a persistent or significant disability/incapacity
- Any other important medical event that may not result in death, be life threatening, or require
 hospitalization, may be considered a serious adverse experience when, based upon appropriate
 medical judgment, the event may jeopardize the subject and may require medical or surgical

intervention to prevent one of the outcomes listed above. Examples of such medical events include allergic bronchospasm requiring intensive treatment in an emergency room or at home, blood dyscrasias or convulsions that do not result in inpatient hospitalization, or the development of drug dependency or drug abuse.

All SAEs will be:

- recorded and reported appropriately
- followed through resolution by a study clinician
- reviewed and evaluated by a study clinician

9.0 Study Withdrawal/Discontinuation

A study subject will be discontinued from participation in the study if any of the following occur:

- Unacceptable toxicity or serious adverse event
- Intercurrent illness, or other medical condition or situation occurs such that continued
 participation in the study would not be in the best interest of the subject in the opinion of the
 treating investigator
- Development of any exclusion criteria
- Subject withdrawals consent to continue in the research for any reason
- Vaginal bleeding of postmenopausal women on treatment cream

Handling of Withdrawals

Subjects who are agreeable may either undergo an exam and exit interview or complete the study procedures as previously described and completed in Study Visit 1 at the time of withdrawal from the study.

If a subject withdraws, a replacement subject may be recruited.

10. Statistical Considerations

This study will be a placebo-controlled, single center study with 3 arms of women planning on undergoing surgery for pelvic organ prolapse.

The primary outcome will be vaginal epithelial thickness based on OCT measures. Findings of collagen and elastin scores, epithelial/stromal/muscularis thickness, cytokines, MMPs, inflammatory cells, and receptors will be also compared between groups. Appropriate statistical analysis for ordinal (e.g. scores) and continuous (e.g. thickness) data will be applied, including tests to determine normality (Shapiro-Wilk) and analysis with ANOVA if criteria are met (e.g. normal, continuous). If ANOVA criteria are not met, then Kruskal-Wallis will be performed for non-normal, ordinal (e.g. scores) data sets.

Power Analysis

Preliminary and historical data are available for OCT thickness, therefore power analysis was based on differences in the OCT thickness mean difference between groups of 40 micrometers with standard deviation 18, and 80% power. Based on T-test and Bonferonni correction (alpha/number of tests = 0.025) for 2 comparisons (1. postmenopausal treatment vs placebo and 2. reproductive age women at 2 different stages of the cycle), five subjects were calculated to be needed per arm to be able to reject

the null hypothesis that the population means of the groups are equal. For example, the postmenopausal group with no estrogen is expected to have epithelial thickness of 100um, the postmenopausal group that receives estrogen is expected to have epithelial thickness of 180um, and the reproductive age women are expected to have epithelial thickness of 240um at follicular phase and 200um at the luteal phase.

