5.0 Study Procedures

Postmenopausal Women

Study Visit 1

Within approximately 30 days of the scheduled surgery date, the postmenopausal subjects will come to the Pelvic Health Clinic at Victory Lakes to have an optical coherence tomography (OCT) scan and pelvic floor (endovaginal) ultrasound.

Both of these tests involve a vaginal probe being inserted in the vagina to collect pelvic organ and tissue images. The OCT produces higher resolution 3-dimensional images and takes 10-15 minutes or less and the endovaginal ultrasound takes about 30-45 minutes.

At this visit, up to 20ml of blood may be drawn for serum hormone levels of estradiol and testosterone, DHEA and androstendione.

Subjects will complete Uro Gyn Clinical Intake Form if not previously within 3 months. The Intake Form includes the following questionnaires: UDI-6, POPDI-6, CRADI-8, PFIQ, PISQ-12 (see protocol appendix for questionnaries).

Subjects will be randomized to placebo or estrogen vaginal cream.

Subjects will be provided with a topical vaginal cream to use daily until 2 days prior to your scheduled surgery date (4-6 weeks). Subjects will apply 0.5 gram of the study vaginal cream daily. Subjects will be given a study diary as a reminder and to record usage and will return their spent tube of cream for weighing as a measure of compliance.

Study Visit 2

Subject will return within a week prior to schedule surgery. Subjects will repeat the OCT, pelvic floor ultrasound and the questionnaires as done in Study Visit 1. Up to 20ml of blood may be drawn to repeat serum hormone levels of estradiol and testosterone, DHEA and androstendione.

Premenopausal Women

Study Visit 1

Premenopausal subjects will have their studies visits 1 scheduled in order to coincide with the subject's follicular or luteal phase of their menstrual cycle. Study visit 2 will be scheduled in order to coincide with opposite phase from study 1.

Premenopausal subjects will come to the Pelvic Health Clinic at Victory Lakes to have an optical coherence tomography (OCT) scan and pelvic floor (endovaginal) ultrasound.

Both of these tests involve a vaginal probe being inserted in the vagina to collect pelvic organ and tissue images. The OCT produces higher resolution 3-dimensional images and takes 10 minutes or less and the endovaginal ultrasound takes about 30 minutes.

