After excision, vaginal tissue will be sectioned into ~3mm pieces and preserved for analysis in formalin, RNALater, and frozen at -80C for future analysis. Formalin preserved sections will be paraffinembedded and stained with H&E (epithelium, stroma, muscularis assessment), Masson's trichrome (collagen, vessel endothelium), Hart's (elastin), or IHC stained for MMPs, estrogen, progestin, and testosterone receptors and CD68 (macrophage). A trained pathologist will interpret the images and provide grading of findings of epithelium, muscularis, collagen, elastin, and IHC findings for presence of MMPs, hormone receptors, and macrophages. Fresh tissue will also be imaged using noninvasive imaging with optical coherence tomography (epithelial and stromal thickness) and multiphoton/SHG imaging (collagen structure) through collaboration with the CBME. Samples in RNALater will be shipped to Oak Crest Institute of Science for evaluation of the transcriptome.

Oak Crest Institute of Science will provide testing and analysis for this study. In addition, coded specimens and data (not having personal identifiers) may be used in ongoing collaborative research with [name] of Oak Crest.

Ultrasound and OCT

Pelvic floor ultrasound will be performed using a standard clinical BK ultrasound system with abdominal, endovaginal, and 3D rotational (vaginal) probes. OCT imaging will be performed using an FDA-approved Niris OCT system (Imalux, Cleveland, OH). OCT images will be collected by direct tissue contact with the 2.7mm diameter probe that will be covered with a sterile disposable sheath and cleaned between use with Cidex. OCT images will be obtained using guidance with a colposcope and a magnetic (GPS) positioning system to record the location of the images collected. Digital images of the cervix and vagina will also be obtained with a digital camera for localization of images.

Parameters measured by ultrasound will include: vaginal thickness, muscularis thickness/volume, vaginal and uterine blood flow (flow and resistive index), levator ani muscle thickness/volume, uterine/cervical descent. Parameters measured by OCT will include vaginal epithelial and stromal thickness. Women will be measured before vaginal treatment with estrogen and 4 weeks after estrogen (or no estrogen) treatment.

The excised tissue will also be evaluated with high resolution imaging methods of OCT and multiphoton/second harmonic generation.

Medical Record Review

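### Section 10 gives the Visit 1 OCT thickness no stated role in the estrogen-placebo comparison; adjusting for it by ANCOVA is a cheap possible gain in precision, not the repair of an error

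*Combined protocol and SAP*

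**What the plan says.** Section 10 states "The primary outcome will be vaginal epithelial thickness based on OCT measures". The analysis it names is "analysis with ANOVA if criteria are met (e.g. normal, continuous"), and otherwise "If ANOVA criteria are not met, then Kruskal-Wallis will be performed for non-normal, ordinal (e.g. scores) data sets". It mentions no covariate, change score or visit. The Power Analysis works with a t-test and with absolute levels: 100 µm without estrogen, while "the postmenopausal group that receives estrogen is expected to have epithelial thickness of 180um".

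Section 5.0 supplies a baseline. Postmenopausal women have OCT at Study Visit 1, before the cream. At Study Visit 2, "Subjects will repeat the OCT, pelvic floor ultrasound and the questionnaires as done in Study Visit 1". Under Ultrasound and OCT: "Parameters measured by OCT will include vaginal epithelial and stromal thickness", and "Women will be measured before vaginal treatment with estrogen and 4 weeks after estrogen (or no estrogen) treatment". Under Vaginal Tissue Analysis there is one further OCT reading, on excised tissue: "Fresh tissue will also be imaged using noninvasive imaging with optical coherence tomography (epithelial and stromal thickness").

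Section 2.0 names tissue inflammatory cytokines as the primary outcome. What follows assumes that Section 10 governs.

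**The concern.** A pre-treatment measurement of the primary variable is normally the most useful covariate in a small randomised comparison. Here it exists for every randomised woman, yet the plan does not say how, or whether, it enters the analysis.

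Two things are at stake. The first is the width of the interval: Section 2.0 says the study is to feed a grant application, so the estimate and its precision are a main product. The second is chance imbalance at baseline in arms of 5 to 10 women. The type I error of the planned test is not at stake.

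**Working it through.** **Inputs.** From Section 10: SD 18 µm, alpha 0.025 per comparison, planning difference 40 µm, 5 per arm, and expected levels of 100 and 180 µm (difference 80 µm). From Section 3.0: up to 30 women, which in three equal groups (Section 4.0) is 10 per arm. Assumed: visit correlation ρ from 0 to 0.8, a two-sided test, equal variances and, for step 5 only, SD 18 µm at Visit 1.

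**1. The plan's own figure.** The normal approximation gives n = 2·[18·(2.241 + 0.842)/40]² = 3.85, so 4 per arm. The noncentral t gives 5 per arm one-sided (86.7% power) and 6 two-sided (86.6%; 76.0% at 5). The stated 5 is reproduced exactly by the one-sided t-test.

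**2. Unadjusted comparison of Visit 2.** SE = 18·√(2/n) = 11.38 µm at 5 per arm and 8.05 µm at 10. Mean 97.5% half-width = t(0.9875, df)·SE·c, where c is the mean of s/σ for the error degrees of freedom.
- t-test, 5 per arm, 8 df: 2.752·11.38·0.969 = 30.4 µm; power 76.0% at 40 µm and 99.98% at 80 µm.
- Pooled three-group ANOVA contrast, 5 per arm, 12 df: 2.560·11.38·0.979 = 28.5 µm; power 81.5% at 40 µm and over 99.9% at 80 µm.
- 10 per arm: t-test (18 df) 19.4 µm and 99.1% at 40 µm; ANOVA (27 df) 18.9 µm and 99.4%.

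**3. ANCOVA on Visit 1, two randomised arms.** Estimate = Δy − b·Δx, with b the pooled within-arm slope. SE = √{[RSS/(2n − 3)]·[2/n + Δx²/Sxx]}. Results are from 200,000 simulated trials per setting.

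| ρ | 5 per arm: half-width (µm) | power at 40 µm | power at 80 µm | 10 per arm: half-width (µm) | power at 40 µm |
|---|---|---|---|---|---|
| 0 | 33.5 | 67.4% | 99.54% | 20.1 | 98.5% |
| 0.3 | 32.0 | 71.6% | 99.71% | 19.1 | 99.2% |
| 0.4 | 30.7 | 75.0% | 99.79% | 18.4 | 99.5% |
| 0.5 | 29.0 | 79.8% | 99.88% | 17.4 | 99.8% |
| 0.6 | 26.8 | 85.6% | 99.94% | 16.1 | 99.9% |
| 0.7 | 23.9 | 92.3% | 99.97% | 14.3 | >99.9% |
| 0.8 | 20.1 | 97.8% | 99.99% | 12.0 | >99.9% |

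Type I error of ANCOVA is 0.024 to 0.025.

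**4. Break-even and worst cost.**
- The half-widths cross at ρ of about 0.42 (t-test) or 0.52 to 0.53 (ANOVA) at 5 per arm, and about 0.26 or 0.33 at 10 per arm.
- Cost at ρ = 0, 5 per arm, 40 µm: 76.0 − 67.4 = 8.6 points against the t-test, or 81.5 − 67.4 = 14.1 against ANOVA. Half-width: 33.5 − 30.4 = 3.1 µm, or 33.5 − 28.5 = 5.0 µm.
- Cost at 80 µm: 99.98 − 99.54 = 0.44 points against the t-test, and under 0.5 against ANOVA.
- Cost at ρ = 0, 10 per arm, 40 µm: 0.6 or 0.9 points, and 0.7 or 1.2 µm.

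**5. Chance imbalance.** The SD of the baseline difference between arms is 11.4 µm at 5 per arm and 8.0 µm at 10. It exceeds 10 µm in either direction in 38% and 21% of trials. A 10 µm imbalance moves the unadjusted estimate by about ρ·10, that is 3, 5 or 7 µm at ρ = 0.3, 0.5 or 0.7.

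**The case against.** The strongest reply is that nothing is broken and the remedy can do harm at the planned minimum size. That is partly right. With 5 per arm, ANCOVA spends one of 8 error degrees of freedom and widens the interval if the correlation is low. If the correlation is 0.2 under estrogen and 0.6 under placebo, there is no gain over the t-test (half-width 30.6 µm, power 75% at 40 µm). Unequal slopes are plausible, since Section 1.0 describes a blunted estrogen response in long-deprived cells, and 5 per arm cannot check them well. The cost is also larger against the three-group ANOVA that Section 10 names than against the t-test used for its power.

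Three other replies stand:
- The power figures at 40 µm matter little here. In Section 10's example the 40 µm gap is between cycle phases (240 versus 200 µm), and estrogen versus placebo is expected to differ by 80 µm.
- Randomisation keeps the unadjusted estimate unbiased, and its interval already allows for chance imbalance.
- If normality fails, Kruskal-Wallis takes no covariate, so Visit 1 drops out again.

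Two stronger readings are tempting. A reader might infer that Section 10 discards Visit 1. It is only silent: it promises appropriate analysis and does not rule out ANOVA on change. A reader might also infer that the excised-tissue reading could serve as the primary value. The other planned comparison is of two cycle phases in the same women, which only in vivo scans at two visits can supply, because tissue is taken once. The documents therefore already point to the in vivo scan.

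These replies reduce the point but do not remove it. At 80 µm ANCOVA power stays above 99.5% whatever the correlation, and at 10 per arm the worst cost is about 1 point and 1 µm.

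**Conclusion.** The point holds as a low-cost precision improvement, conditional on OCT thickness being primary. The documents do not support calling the planned comparison invalid, biased or underpowered at the difference expected for this contrast.

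The size depends on a visit correlation that the documents do not give. At 5 per arm and a correlation of 0.7, the half-width falls from 30.4 µm (t-test) or 28.5 µm (ANOVA) to 23.9 µm; at zero it rises to 33.5 µm. At 10 per arm, 0.7 gives 14.3 µm against 19.4 or 18.9 µm. The figures also assume SD 18 µm, normality and a common slope. Confidence is medium: the gap in the text is plain, but the benefit at 5 per arm is not assured.

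**What to change.** In Section 10, state that the primary estrogen-placebo comparison uses Visit 2 in vivo OCT epithelial thickness, analysed by ANCOVA on arm with Visit 1 thickness as covariate, and report the unadjusted difference beside it. Keep the Kruskal-Wallis fallback on Visit 2 values. Naming the in vivo scan is a clarification only. The change does not apply to the within-woman cycle-phase comparison. Separately, reconcile Section 10 with the cytokine primary outcome in Section 2.0.

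The cost is one or two sentences and no new data. The statistical price is the low-correlation loss set out in step 4 of the working. Reporting the unadjusted result alongside lets readers see whether that loss occurred.

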At this visit, up to 20ml of blood may be drawn for serum hormone levels of estradiol and testosterone, DHEA and androstendione. Urine or serum pregnancy test will be performed for patients at risk of pregnancy at the discretion of the study gynecologist.

Subjects will complete Uro Gyn Clinical Intake Form if not previously within 3 months. The Intake Form includes the following questionnaires: UDI-6, POPDI-6, CRADI-8, PFIQ, PISQ-12 (see protocol appendix for questionnaries).

Study Visit 2

Subject will return within a week prior to schedule surgery. Subjects will repeat the OCT, pelvic floor ultrasound and the questionnaires as done in Study Visit 1. Up to 20ml of blood may be drawn to repeat serum hormone levels of estradiol and testosterone, DHEA and androstendione.

Surgical Tissue Collection

After anesthesia and prior to vaginal preparation for surgery, vaginal fluid (secretions) will be collected similar to getting a pap smear and vaginal rinse with saline will be performed and up to 30ml of the rinse material or lavage will be collected for research to look at cytokines and vaginal microflora.

The surgical tissue that is excised and removed is standard for the surgery performed, and typically this tissue is discarded after surgery. The tissue collected for this research is discarded surgical tissue, about 2-4 postage stamps in size, depending on whether anterior and/or posterior surgical repair is performed.

The surgery will proceed as scheduled and tissue from the vagina will be collected and processed for further tissue analysis. The tissue collected will be the tissue that is typically discarded during the surgery.

Vaginal Secretion and Vaginal Fluid Analysis

Vaginal secretions and lavage fluid will be transported to [name] lab and to Oak Crest Institute of Science and will be evaluated for cytokines, including IL-6, TNF- α , TNF- β , evidence of inflammatory cells, and vaginal microflora using an extended qPCR panel developed with an ITS Novel Methods Grant ([name], [name], 2012).

Vaginal Tissue Analysis

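### Section 10 sizes the study on two t-tests at 0.025, but its analysis paragraph names only ANOVA or Kruskal-Wallis and does not tie them to those two comparisons, one of which is within-woman

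*Combined protocol and SAP*

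**What the plan says.** Section 10 names OCT vaginal epithelial thickness as the primary outcome of a three-arm, placebo-controlled study. The other outcomes "will be also compared between groups". For continuous data the method is a Shapiro-Wilk check, then "analysis with ANOVA if criteria are met (e.g. normal, continuous"). Kruskal-Wallis is the fallback for non-normal and ordinal data. The paragraph introduces these methods as examples of appropriate analysis. It gives no contrast, no paired or repeated-measures method and no alpha.

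The Power Analysis paragraph of the same section uses a t-test with a Bonferroni-corrected 0.025 for two comparisons: "1. postmenopausal treatment vs placebo and 2. reproductive age women at 2 different stages of the cycle". It assumes a 40 um difference, SD 18 and 80% power, finds five subjects per arm, and frames the aim as rejecting "the null hypothesis that the population means of the groups are equal". The expected means are 100 um without estrogen and 180 um with it, and "the reproductive age women are expected to have epithelial thickness of 240um at follicular phase and 200um at the luteal phase".

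Section 5.0 (Premenopausal Women) sets Visit 1 in the "follicular or luteal phase of their menstrual cycle" and adds: "Study visit 2 will be scheduled in order to coincide with opposite phase from study 1". Each premenopausal woman therefore supplies both phase readings.

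**The concern.** The tests that size the study are not the tests named for analysing it. Two consequences follow if the analysis paragraph is applied literally.

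- **Randomised comparison.** Only the two postmenopausal arms are randomised (Section 4.0). A three-arm omnibus test asks whether any of three means differ, and the premenopausal arm is expected to differ greatly from placebo. A significant result would carry no information about estrogen.
- **Cycle phase.** The two readings come from the same women. Kruskal-Wallis and between-group ANOVA treat them as independent, so the test would not run at 0.025, and no paired method is named to replace it.

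At stake is whether the primary outcome yields an interpretable answer to either sized question, or whether the analyst must choose the test after the data are in, with about five women per arm.

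**Working it through.** **Inputs.** From Section 10: n = 5 per arm, SD = 18 um, alpha = 0.025 per comparison; means 100 (placebo), 180 (estrogen), 200 (luteal) and 240 (follicular). From Section 5.0: both phases are measured in the same women. Assumed, because the documents do not give it: within-woman correlation rho. Tests are taken as two-sided, since sidedness is not stated.

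**1. The plan's own figure.** For a two-sample t-test, the noncentrality is 40 / (18 × √(2/5)) = 3.51.
- Two-sided 0.025, 8 df: critical t 2.752, power 0.760 at n = 5; 0.866 at n = 6.
- One-sided 0.025: power 0.745 at n = 4; 0.867 at n = 5, so five per arm.
- Paired, two-sided 0.025, SD of differences 18: power 0.639 at n = 4; 0.859 at n = 5, again five.

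Five per arm is reproduced under reasonable readings. The sample size is not the error.

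**2. Three-arm omnibus F.** lambda = 5 × Σ(mean − grand mean)² / 18², with 2 and 12 df; critical F is 3.89 at 0.05 and 5.10 at 0.025.

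| Premenopausal mean | lambda, no estrogen effect (100/100) | lambda, planned effect (100/180) |
|---|---|---|
| 200 | 102.9 | 86.4 |
| 220 (midpoint, assumed) | 148.1 | 115.2 |
| 240 | 201.6 | 152.3 |

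Example, 100/100/200: the grand mean is 133.3, the squared deviations sum to 6,667, and 5 × 6,667 / 324 = 102.9. Power exceeds 0.9999 in all six cells at both levels. Kruskal-Wallis with no estrogen effect rejected in 100% of 20,000 simulated trials at a premenopausal mean of 200 or 240. By contrast, the estrogen-placebo t-test at 0.025 rejects 2.5% of the time when estrogen does nothing.

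**3. Phase readings treated as independent groups.** Simulated rejection of a true null at nominal 0.025, five women:

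| rho | two-group ANOVA | Kruskal-Wallis | paired t |
|---|---|---|---|
| 0.25 | 1.4% | 0.9% | 2.5% |
| 0.5 | 0.6% | 0.4% | 2.5% |
| 0.75 | 0.1% | 0.1% | 2.5% |

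For a true 40 um difference, Kruskal-Wallis power is 64% to 66% over this range. The unpaired t-test has 76% at rho = 0 and 78%, 80% and 82% at 0.25, 0.5 and 0.75.

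**4. Paired t-test.** SD of the difference = 18 × √(2(1 − rho)); noncentrality = 40 / (SD of difference / √5); 4 df, critical t 3.495.

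| rho | SD of difference | noncentrality | power |
|---|---|---|---|
| 0 | 25.5 | 3.51 | 57% |
| 0.25 | 22.0 | 4.06 | 70% |
| 0.5 | 18.0 | 4.97 | 86% |

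Power reaches 80% at rho of about 0.41.

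**5. Estrogen versus placebo at the expected 80 um.** Noncentrality = 80 / 11.38 = 7.03; power is over 99.9%.

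**6. Rank tests.** Smallest two-sided p: Mann-Whitney 5 v 5, 2/252 = 0.0079. Signed-rank, 2/2^n: 0.0625 with 5 women, 0.031 with 6, 0.0156 with 7.

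**The case against.** The methods are given as examples of appropriate analysis, so the list is not closed, and the next paragraph names the t-test, the alpha and both comparisons. A two-group ANOVA of estrogen against placebo is the t-test. A planned contrast in the three-arm model would also isolate estrogen; if the arms share one variance, its 12 error df give 81% power for 40 um. A repeated-measures ANOVA would fit the phase data. All of this stands. It makes the intended comparisons inferable, but no sentence selects any of these forms, and Kruskal-Wallis has no form that fits paired readings. Kruskal-Wallis would reach OCT thickness only if the normality check failed.

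A reader might infer four stronger things that the documents do not support:

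- *The plan will read the omnibus p-value as the estrogen effect.* No passage proposes that. The step 2 result describes what follows if it were read so.
- *The phase analysis inflates false positives.* It does the opposite. At low correlation the unpaired t-test also has more power than the paired one (76% against 57% at rho = 0).
- *The sized comparisons were not prespecified.* They and their alpha are written in advance.
- *The plan must prescribe a phase and visit for a post- versus premenopausal contrast.* That is not one of the two sized comparisons, and choosing its form is a separate design matter.

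Section 2.0 names tissue cytokines as the primary outcome. That conflict with Section 10 needs settling separately; this point concerns OCT thickness as Section 10 states it.

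**Conclusion.** The mismatch is real and should be corrected; it is not fatal. Read literally as a three-arm test, the named analysis rejects with probability above 0.9999 with or without an estrogen effect, so it cannot answer the randomised question. That rests on the plan's own means, SD 18, five per arm, normality and equal variances. Applied to the phase readings, a between-group ANOVA is conservative: 1.4%, 0.6% and 0.1% against 2.5% at assumed correlations of 0.25, 0.5 and 0.75. The documents give no correlation, so the size of that loss, and whether pairing gains or loses power, cannot be settled from them.

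**What to change.** In the analysis paragraph of Section 10, state for OCT epithelial thickness, each at the 0.025 already used for sizing:

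1. **Estrogen versus placebo at Visit 2** in the randomised women is a primary test, by two-sample t-test, with Mann-Whitney as the rank fallback.
2. **Follicular versus luteal within premenopausal women** is a primary test, by paired t-test. Note that a signed-rank fallback can reach 0.025 only with 7 or more women. Section 3.0 sets at least 5 reproductive-age completers, so 7 is possible but not assured.
3. **The three-arm ANOVA or Kruskal-Wallis** is not evidence of an estrogen effect.

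Say also whether 0.025 is two-sided, as assumed here.

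**Cost.** Wording only; no added women or visits. The downside is power. With 5 women the paired test has 57%, 70% and 86% for 40 um at correlations of 0, 0.25 and 0.5, and meets the stated 80% only from about 0.41. With 5 or 6 women there is no usable rank fallback for phase. The two-sample test has 76% for 40 um, below the stated 80%, but over 99.9% for the 80 um that the plan expects from estrogen.
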